8.7.2 Pharmacokinetic, pharmacodynamic and Immunogenicity parameters

These procedures are applicable only to patients randomized on GRASPA treatment arm and they consist in the following tests:

- Amino acids levels: asparagine, aspartate, glutamine, and glutamate
- Whole blood asparaginase
- Anti-L-asparaginase antibodies

The Appendix 3: Samples preparation for centralized analyses summarizes parameters, procedures and central laboratories involved (a lab manual also is also edited and provided to investigational center).

NOTE: on the scheduled days for GRASPA administration, samples should be taken at least 5 minutes prior administration.

8.8 Patients Quality of Life

Patients will complete quality of life (QoL) questionnaire (EORTC QLQ-C30, version 3, Appendix 4) at each visit.

Also the number of transfusions (packed RBC or platelet) received by the patient will be recorded along the study as well as hospitalization (except scheduled for protocol visit).

8.9 Biomarker assessments

Bone marrow biopsy/aspirate will be collected at study entry and will be analyzed for biomarker analysis of potentially relevant biomarkers, utilizing proteomic, and transcriptomic techniques. Assays designed to evaluate biomarkers that may correlate with clinical outcome will be performed, including:

- Asparagine synthetase (ASNS) expression by two different methods: real-time qRT-PCR for the quantification of ASNS mRNA and western-blot for the quantification of ASNS protein expression (performed at The University of Texas MD Anderson Cancer Centre and Erytech Pharma respectively).
- Mutational analyses and detection of gene amplification of relevant oncogenes, e.g FLT3, NPM1, IDH or KIT
- Depending on tissue availability, additional assays may be performed, including immunohistochemistry (IHC), gene expression profiling, and transcriptomic profiling.
- Other potential biomarkers, as new scientific data emerge.

Cells isolated from bone marrow by ficoll will be also cultured in presence of L-asparaginase. *In-vitro* sensitivity to L-asparaginase will be assessed at ERYTECH Pharma by measuring the cytotoxicity using a colorimetric assay.

Assessments could be repeated on further bone marrow aspirate if possible.

Please refer to Appendix 3 (Samples preparation for centralized analyses) as well as to lab manual for details regarding procedure of samples collection, handling, storage, shipping and central laboratory involved.

8.10 Study visits assessments and procedures

• Inclusion Visit (within max 4 weeks before treatment initiation):

During the inclusion visit, the following procedures/assessments will be performed:

- Patient information about potential study participation and obtaining the signed informed consent before any study related procedures;
- Patient demographics: date of birth, gender;
- ECOG performance status
- AML characteristics and assessment (see section 8.6): qualitative and quantitative parameters, primary diagnostic date, baseline values for bone marrow blast count, cytogenetic analysis, FAB and WHO classifications, including extramedullary AML assessment
- Medical history (relevant for the study condition) and concomitant medications
- General physical examination by systems and organs, including routine ECG, weight and height measurements
- Biological assessment (see section 8.7.1 for detailed items): date of sample taken; assessed and signed anonymized lab reports must be sent to sponsor/representatives Inclusion and exclusion criteria validation
- Patient registration in IWRS system
- Patient randomization if all criteria are met.
- Subsequent visits : from visit 1 onwards:
 - Disease evaluation (AML) (see section 8.6)
 - Clinical assessment: vital signs (height, weight, pulse, blood pressure systolic and diastolic), performance status (ECOG score), physical examination findings
 - Study treatment administration (low-dose cytarabine +/- GRASPA): details on date and time of administration are required
 - Patient quality of life: survey EORTC QLQ-C30, transfusion needs, hospitalizations from any cause (except scheduled protocol visit)
 - Biological assessment at D1, D5, D9, D13, D18, D23, D27 (see section 8.7.1 and table 4 for detailed items) instructions to be provided to patient in case of lab testing outside the site hospital; assessed and signed anonymized lab reports must be sent to sponsor/representatives as soon as possible after sampling
 - PK-PD and immunogenicity testing (see section 8.7.2, Table 4 and 5 and Appendix 3 for detailed instructions) only patients on arm B (under GRASPA treatment)
 - IAST (Irregular Antibodies Screening Test) at D9 only patients on arm B (under GRASPA treatment)
 - Review and assessment of any adverse event (refer to section 11 for details)
 - Record of any change in concomitant medications
 - Distribution of patient diary and instructions provided to patients for completion for each visit
 - Collection and Review of previous patient diary completed
- End of study treatment
 - Disease evaluation (AML) (see section 8.6)
 - Clinical assessment: vital signs, performance status (ECOG score), physical examination findings

- Patient quality of life: survey EORTC QLQ-C30, transfusion needs, hospitalizations from any cause (except scheduled protocol visit)
- Primary reason for treatment termination
- Subsequent AML treatment if any
- Collection and Review of previous patient diary completed
- Review and assessment of any adverse event (refer to section 11 for details)
- Follow-up visit after end of study treatment (every 3 months +/- 2 weeks after End of Treatment visit ex. M3, M6, M12...)
 - Disease evaluation, in the case relapse/recurrent status had not already occurred and the patient was discontinued from the treatment for other reason
 - Patient quality of life: survey, transfusion needs, hospitalizations from any cause (except scheduled protocol visit)
 - Clinical assessment: Survival status
 - Review and assessment of any adverse event (refer to section 11 for details)
 - At minimum, a phone call will be performed 4 months (+/- 1 week) after end of treatment, for safety assessments

8.11 End of study treatment

Patients will stop study treatment in following situations:

- Disease relapse or presence of a resistant disease, unless the investigator considers that the patient has a clinical benefit from continuing the treatment. In this case, the investigator should continue to perform the same study visits as long as considered clinical beneficial.
- Occurrence of GRASPA-related toxicity, such as:
 - Grade 3 or 4 pancreatic toxicity
 - o Grade 3 or 4 hepatic toxicity, allergic reaction, or coagulation event
 - o other non-hematologic Grade 4 toxicity

Patient assessment should continue as planned until evidence of relapse or presence of a resistant disease, in which case, patient will be followed up for survival.

- Patient unwilling to continue
- No evidence of study treatment benefit at investigator's decision

9. Investigational product: GRASPA

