Treatment discontinuation	 Patients will discontinue study treatment in the following situations: Disease relapse or presence of a resistant disease, unless the investigator considers that the patient has a clinical benefit from continuing the treatment. In this case, the investigator should continue to perform the same 								

– CONFIDENTIAL –										
	study visits as long as considered clinical beneficial.									
	Occurrence of GRASPA-related toxicity, such as:									
	• Grade 3 or 4 pancreatic toxicity									
	 Grade 3 or 4 hepatic toxicity, allergic reaction, or coagulation event 									
	 other non-hematologic Grade 4 toxicity 									
	Patient assessment should continue as planned until evidence of relapse or presence of a resistant disease, in which case, patient will be followed up for survival.									
	Patient unwilling to continue									
	No evidence of study treatment benefit at investigator's decision									
Statistical plan	Sample Size									
	The sample size calculation has been based on the original primary efficacy endpoint (PFS) and a study that included an interim analysis for futility. We assumed 75% improvement in median PFS in the GRASPA plus low-dose cytarabine group compared to median PFS in the low-dose cytarabine group (control). With a two-sided 5% level significance test and a power of 80%, taking into account the unbalanced group size (2 : 1) and interim analysis a total of 123 patients should be enrolled (82 in the GRASPA plus low-dose cytarabine and 41 in the low-dose cytarabine group).									
	Analysis plan									
	The primary objective of the trial is to estimate whether GRASPA plus low-dose cytarabine is more promising than low-dose cytarabine alone with respect to OS in subjects 65-85 years old, with newly diagnosed AML unfit for intensive chemotherapy. The study however is not powered explicitly for OS and statistical significance in favor of GRASPA plus low-dose cytarabine is not anticipated. A decision as to whether GRASPA appears to be a promising drug in this indication will be based on the numerical values for the hazard ratio for OS. A hazard ratio of ≤ 0.80 will indicate a 20% numerical reduction in the death rate on average over time in the GRASPA group compared to control.									

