8.5.4 Dosage modifications for GRASPA

- If patient cannot receive GRASPA, for another reason than an adverse event, treatment may be postponed no later than one week after the initial scheduled day. A minimum two weeks interval between GRASPA infusions must be insured.
- In case of allergic reaction during administration, stop the administration immediately and then to administer the necessary symptomatic treatments, according to standard of care. Further administration of GRASPA will be at investigator judgment, considering possibility of premedication anticipated for such case.
- In case of any Grade 3 or 4 adverse event related to GRASPA occurring in two successive infusions, GRASPA should be discontinued.
- In the event of bilirubin levels >3 times upper limit of normal or transaminase levels >10 times upper limit of normal, treatment with GRASPA should be discontinued.

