9.5 Precaution for use

Anaphylaxis or serious allergic reactions: Patients should be constantly monitored during the infusion and at least one hour after the end of the infusion. Discontinue GRASPA with serious allergic reactions.

Coagulation disorders: Blood count and clotting profile should be monitored before and during treatment with GRASPA. In cases of anti-thrombin III deficiency, administration of anti-thrombin III concentrate is preferable to transfusion of fresh frozen plasma (FFP) as it could counteract the GRASPA activity.

Hepatotoxicity: Hepatic enzymes should be monitored before and regularly during treatment with GRASPA. Treatment with GRASPA should be discontinued in the event of bilirubin levels >3 times upper limit of normal or transaminase levels >10 times upper limit of normal.

Pancreatitis: Serum lipase and amylase should be monitored regularly. Treatment with GRASPA should be discontinued in patients with Grade 4 pancreatitis.

Glucose intolerance: L-asparaginase may cause hyperglycemia and patients with diabetes may have aggravation of their condition. Blood glucose levels should be monitored regularly.

Cardiac or renal impairment: Patients should be monitored for evidence of volume overload. The speed of infusion of GRASPA should be slowed as needed.

If a patient receives a blood transfusion between the prescription of GRASPA and its administration, new compatibility tests must be performed.

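### The protocol's stop rules for GRASPA toxicity disagree: a first Grade 3 pancreatic event ends dosing in the synopsis and 8.11, but not in 8.5.4 or 9.5

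*Protocol*

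**What the plan says.** Three parts of the protocol govern when GRASPA stops for toxicity.

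**Synopsis and 8.11.** The synopsis opens its list with "Patients will discontinue study treatment in the following situations", and 8.11 gives the same list. For GRASPA-related toxicity the examples are "Grade 3 or 4 pancreatic toxicity", "Grade 3 or 4 hepatic toxicity, allergic reaction, or coagulation event", and other non-hematologic Grade 4 toxicity. The list is illustrative, and a first occurrence is enough. Section 8.11 adds "Patient assessment should continue as planned until evidence of relapse or presence of a resistant disease", after which the patient is followed for survival.

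**8.5.4, dosage modifications.** The general rule is "In case of any Grade 3 or 4 adverse event related to GRASPA occurring in two successive infusions, GRASPA should be discontinued". For an allergic reaction during administration the infusion is stopped and treated, and then "Further administration of GRASPA will be at investigator judgment, considering possibility of premedication anticipated for such case". No grade limit is given. The hepatic trigger is worded "In the event of bilirubin levels >3 times upper limit of normal or transaminase levels >10 times upper limit of normal".

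**9.5, precautions.** "Treatment with GRASPA should be discontinued in patients with Grade 4 pancreatitis". Serious allergic reactions also end GRASPA, and the hepatic limits are those of 8.5.4. For coagulation there is monitoring and antithrombin advice but no stop rule.

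Section 9.12 refers the reader to 8.11 for end of study treatment. Section 8.4 cites 8.5.4 and 8.11 together. Neither says which prevails when they differ.

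**The concern.** A site that looks up GRASPA dosing after a toxic event will naturally open 8.5.4, which does not point to 8.11. A site that looks up end of treatment will open 8.11. The two can act differently on the same event, and each would be following the protocol as written.

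The patients are 65 to 85 and mostly enrolled because they are unfit for intensive chemotherapy. Section 5.2.1 itself describes L-asparaginase toxicities as treatment-limiting in frail populations. What is at stake is whether a patient is re-exposed. GRASPA is given on Day 11 of each 28-day course, so after an event following the first infusion the next is due on Day 11 + 28 = Day 39 (subject to the 3-day course window). Section 8.11 rules that infusion out; 8.5.4 on its own does not. Counts of GRASPA exposure and discontinuation would also mix different site practices.

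**Working it through.** No figure in the plan is at issue, so the check is to take one first, GRASPA-related event at a time and read off what each section requires.

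| First related event | Synopsis and 8.11 | 8.5.4 | 9.5 |
|---|---|---|---|
| Grade 3 pancreatic | Stop | No stop unless in two successive infusions | No stop (threshold is Grade 4) |
| Grade 4 pancreatic | Stop | No stop unless in two successive infusions | Stop if pancreatitis, related or not |
| Grade 3 or 4 allergic, during infusion | Stop | Further doses at investigator judgment, any grade | Stop if serious |
| Grade 3 or 4 coagulation | Stop | Two-infusion rule only | No stop rule |
| Other non-hematologic Grade 4 | Stop | Two-infusion rule only | Silent |
| Grade 3 or 4 hepatic | Stop | Stop at bilirubin >3x ULN or transaminases >10x ULN | Same limits as 8.5.4 |

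The rows are not all of one kind.

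1. **Pancreatic and allergic: different stated rules.** Section 9.5 names a pancreatic grade, and it is not the grade in 8.11. If 8.11 always governed, the 9.5 threshold would add nothing for related events. The allergy bullet in 8.5.4 does more than omit a stop: it allows re-treatment with no grade limit, where 8.11 stops at Grade 3.
2. **Coagulation and other Grade 4: overlap without precedence.** The two-infusion rule covers any related Grade 3 or 4 event, so it includes events for which 8.11 stops at the first. Section 9.5 gives no opposing rule on either.
3. **Hepatic: compatible, but not stated to be so.** A limit in multiples of ULN can stand beside a grade rule. No text says it is an additional stop. Whether the limits match CTCAE grades cannot be checked from the documents.

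As to which grades to adopt, the synopsis agrees with 8.11, and SAP 3.1 uses the same pancreatic, hepatic, allergic and coagulation grades to define limiting toxicity. The secondary safety endpoints in Protocol 4.3.2 also single out Grade 3 or 4 in these classes.

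**The case against.** The best defence is that 8.11 is the termination rule, while 8.5.4 and 9.5 are headed as dose modifications and precautions. Neither uses the words only if, and neither tells a site to continue after a first Grade 3 event. A site that applied every section would meet 8.11 first, and the two-infusion rule would then serve for events 8.11 does not name. Section 9.12, in the same chapter as 9.5, sends the reader to 8.11.

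This is a sensible reading, and the fix adopts it. It also disposes of any claim that all five toxicity classes contradict one another: silence in 9.5 on coagulation or other Grade 4 events is not a rival rule, and the hepatic limits are compatible. But the protocol never states that reading. It also does not reconcile the Grade 4 pancreatitis threshold in 9.5 or the ungraded allergy bullet in 8.5.4 with 8.11.

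A reader might infer more than the documents support:

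- *That patients would certainly be re-infused.* Section 8.5.4 does not require another dose, and 8.11 also allows stopping for patient unwillingness or lack of benefit.
- *That a count of affected patients can be given.* The protocol reports drug-related amylase or lipase elevation in 7 of 26 GRASPA patients (26.9%) in the earlier ALL trial. That is any grade, at ages 1 to 55, with multi-agent chemotherapy. Scaling it to 82 patients says nothing about Grade 3 events.
- *That the IDMC lacked a definition.* Section 11.6 refers only to stopping rules, but SAP 3.1 lists the limiting toxicities for the 30-patient review, and 8.5.4 and 9.5 play no part in that list.
- *That 9.4 is a further on-study stop.* It is a contraindication based on history of Grade 4 hypersensitivity.
- *That one closed, GRASPA-only list would be mere tidying.* Section 8.11 speaks of study treatment, which 8.10 describes as cytarabine with or without GRASPA, and its toxicity list is open. Replacing it with such a list could remove a cytarabine stop and drop unlisted toxicities.

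Timing also limits the practical gain. The SAP reports the IDMC's end-of-recruitment review as done. If dosing has ended, the edit no longer protects patients in this trial, and planned listing 14.3.1.3 shows events leading to withdrawal, not cases where GRASPA continued or the section a site applied.

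**Conclusion.** The point stands as a text inconsistency with safety consequences: the rules are wrong as written. The sections differ outright on pancreatic and allergic toxicity. They overlap without precedence on coagulation and other non-hematologic Grade 4 events, and for hepatic toxicity they leave unstated whether the ULN limits are additional.

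Per patient, the difference is between no further GRASPA and eligibility for the next scheduled infusion. The number of patients concerned is unknown, because the documents give no Grade 3 or 4 rate for these events. The conclusion rests only on reading each rule as written, and on no section being given precedence. It does not touch the sample size, the significance level or the intention-to-treat analysis, and no effect on the survival hazard ratio is claimed: the documents give neither the share of patients who would stop nor the hazard afterwards.

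**What to change.** 1. In 8.5.4, state that the 8.11 criteria apply at the first event and take precedence; that the two-infusion rule covers only related Grade 3 or 4 events not listed in 8.11; and that bilirubin >3x ULN and transaminases >10x ULN are additional stops.
2. In the 8.5.4 allergy bullet, limit re-treatment at investigator judgment to non-serious reactions below Grade 3.
3. In 9.5, replace the pancreatitis rule with: GRASPA-related Grade 3 or 4 pancreatic toxicity, or any Grade 4 pancreatitis. Refer to 8.11. The second limb keeps the present stop, which is not confined to related events.
4. Leave the open list and the study-treatment wording in 8.11 as they are. Whether low-dose cytarabine continues after a GRASPA-related stop is a separate decision for the sponsor.

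The cost is text edits to 8.5.4 and 9.5, with no new data, table or SAP change. The downside is that some patients would stop GRASPA earlier than 8.5.4 or 9.5 alone would require. Section 9.5 would also become stricter than the proposed SPC, with which version 7 aligned it according to Appendix 11.

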9.1 Pharmaceutical form, qualitative and quantitative composition

GRASPA is a dispersion for infusion of eryaspase, packed in transparent PVC bag designed for blood product, containing a single dose for one administration.

Each bag of GRASPA contains:

- Active substance: eryaspase, at a dose equivalent to 100 IU/kg of L-Asparaginase.
- Preservative solution: SAG Mannitol

The Red Blood Cell (RBC) source material is from leukocyte-depleted packed red blood cells, prepared and qualified by a blood bank. Selected RBC source material is compatible with the patient (blood type and results of irregular antibodies screening test).

The final volume of GRASPA bag depends on patient weight.

9.2 Posology

GRASPA is a ready to use suspension designed to be fully injected.

The dose of GRASPA is 100 IU/kg. In this study protocol, patients will receive one infusion of GRASPA on Day 11 of 28-day course of chemotherapy (see section 10.1).

9.3 Packaging and labeling

GRASPA is packaged in PVC (polyvinyl chloride) bags designed for blood product. Three removable segment-tubes are available and attached for checking before administration.

Label statements are specific to the clinical trial, complying with legal requirements for medicinal product. In addition they display specific items necessary for traceability of source cell material and medicinal product (blood group, patient's initials and birthdate). These mentions allow for checking the identity before administration.

9.4 Contra Indications

GRASPA should not be used in the following situation:

- History of Grade 4 hypersensitivty reaction to L-asparaginase
- Pregnancy/breastfeeding (see section 11.4)

9.5 Precaution for use

Anaphylaxis or serious allergic reactions: Patients should be constantly monitored during the infusion and at least one hour after the end of the infusion. Discontinue GRASPA with serious allergic reactions.

Coagulation disorders: Blood count and clotting profile should be monitored before and during treatment with GRASPA. In cases of anti-thrombin III deficiency, administration of anti-thrombin III concentrate is preferable to transfusion of fresh frozen plasma (FFP) as it could counteract the GRASPA activity.

Hepatotoxicity: Hepatic enzymes should be monitored before and regularly during treatment with GRASPA. Treatment with GRASPA should be discontinued in the event of bilirubin levels >3 times upper limit of normal or transaminase levels >10 times upper limit of normal.

Pancreatitis: Serum lipase and amylase should be monitored regularly. Treatment with GRASPA should be discontinued in patients with Grade 4 pancreatitis.

Glucose intolerance: L-asparaginase may cause hyperglycemia and patients with diabetes may have aggravation of their condition. Blood glucose levels should be monitored regularly.

Cardiac or renal impairment: Patients should be monitored for evidence of volume overload. The speed of infusion of GRASPA should be slowed as needed.

If a patient receives a blood transfusion between the prescription of GRASPA and its administration, new compatibility tests must be performed.

9.6 Prescription

GRASPA is manufactured for one patient at a time according to investigator's prescription.

To initiate the manufacture, ERYTECH Pharma should be provided with the documents listed hereafter:

- **Prescription Sheet** indicating patient identifiers as well as his weight, the investigator recipient of the product, the place and the time of delivery. A template of the prescription sheet is available in Appendix 5: Prescription of GRASPA
- Validated Erythrocyte phenotype and **ABO blood group card** with 2 determinations
- an IAST (Irregular Antibody Screening Test) performed at the local immunohematology laboratory, less than 72h prior to GRASPA transfusion

In the event the IAST is positive, or in case of previous or history of positivity, a compatibility test is mandatory. Therefore, a 5 mL sample of patient's blood should be sent to EFS Lyon (Service Immuno-hématologie, Hôpital Edouard Herriot pavillon I, [name]. N° [contact] n° [contact])

